### **4.5 Discontinuations**

#### **4.5.1 Discontinuation of Study Drug/Medication**

The criteria for enrolment must be followed explicitly. If a patient who does not meet enrolment criteria is inadvertently enrolled, that patient should be discontinued from the study drugs/medications, but can be allowed to continue in the study in order to provide the follow-up data needed for the analysis of the entire population. An exception may be granted if the patient, in the opinion of the Investigator, is having benefit from the study drugs/medications. In these rare

cases, the investigator must obtain documented approval from GEICAM to allow the patient to continue to receive the study drugs/medications.

Patients can be discontinued from the study therapy in the following circumstances:

- Patient's own request. The patient is at any time free to discontinue treatment, without prejudice to further treatment.
- Unacceptable toxicity as defined in the protocol.
- Any clinical adverse event (AE), laboratory abnormality or inter-current illness which, in the opinion of the investigator, indicates that continued participation in the study is not in the best interest of the patient.
- Bone marrow findings consistent with myelodysplastic syndrome (MDS)/acute myeloid leukaemia (AML).
- Pregnancy:
  - ✓ Instruct to contact the investigator or study staff immediately if they suspect they might be pregnant.
  - ✓ The investigator must immediately notify GEICAM if a study patient becomes pregnant.
- Tumour progression as defined in the protocol.
- Severe non-compliance with the study protocol by the patient.
- Loss of ability to freely provide consent through imprisonment or involuntarily incarceration for treatment of either a psychiatric or physical (e.g. infectious disease) illness.
- Physician's decision, including need of other anti-cancer therapy, not specified in the protocol.
- Termination of the study by GEICAM.

All permanent treatment discontinuation should be recorded by the Investigator in the eCRF when considered as confirmed.

It is important to discriminate between discontinuation of study treatment only and withdrawal from study (study treatment and follow up).

#### **4.5.2 Discontinuation of Study Sites**

Study Site participation may be discontinued if GEICAM, the investigator or the Independent Ethics Committee (IEC) of the study site judges it necessary for any reason.

#### **4.5.3 Discontinuation of Study**

The study may be discontinued by GEICAM if this is medically reasonable and consistent with applicable regulations of Good Clinical Practice (GCP). Stopping the study for medical reasons may be required if patients experienced adverse reactions under the treatment with the study drug/medication or if new information about the safety or effectiveness of the study drug/medication justifies it.

### **5. STUDY VARIABLES**

#### **5.1 Patient Disposition**

A detailed description of patient disposition will be provided. It will include:

- Summary of patients entered and by site.
- Total number of patients entered.
- Total number of patients enrolled and by site.
- Summary of reasons for patients entered, but not enrolled. This summary will include:
  - Nº of patients not included due to having *BRCA1/2* germline mutations
  - Nº of patients not having methylated *BRCA1* and/or *BRCA2* promoters
  - Nº of patients not having tumor available
  - Nº of patients in which the methylation or germline mutation analysis was not assessable.
- Total number of patients treated and by site.
- Summary of reasons for patients enrolled, but not treated.

A detailed summary of reasons for patient discontinuation from study treatment will be provided.

A summary of all identified important protocol major violations will be provided.

#### **5.2 Patient Characteristics**

Patient characteristics will include a summary of the following:

- Patient demographics.
- Baseline disease characteristics.
- Pre-existing conditions/secondary conditions.

- Prior anti-cancer therapy.

Other patient characteristics will be summarized as deemed appropriate.

Standard descriptive statistics, such as the mean, median, range and proportion, will be used to summarize the patient sample and to estimate parameters of interest. Ninety-five percent confidence intervals will be provided for estimates of interest where possible.

### **5.3 Concomitant Therapy**

A summary of concomitant therapies will be generated in the safety population.

### **5.4 Treatment Compliance**

Treatment information will be collected at each dose administration. The estimate of percent compliance will be given by:

$$\text{Percent Compliance} = \frac{\text{Actual dose administered per week}}{\text{Dose expected to be administered per week}} \times 100$$

No minimal level of compliance will be defined for patient inclusion in efficacy analyses. To be considered compliant patients should have received at least 80% of the planned number of doses. Exploratory analysis of the impact of compliance on selected efficacy endpoints may be performed if deemed necessary.

## **6. ENDPOINTS**

### **6.1 Efficacy Endpoints**

#### **6.1.1 Primary End-point**

Objective Response Rate (ORR) defined as Complete Response (CR) plus Partial Response (PR) according to Response Evaluation Criteria in Solid Tumours (RECIST) version 1.1.

#### **6.1.2 Secondary End-points**

The following secondary end-points will be studied:

- Clinical Benefit Rate (CBR), Duration of Response (DoR), Progression Free Survival (PFS) and Overall Survival (OS).

- Adverse events defined by the NCI-CTCAE (National Cancer Institute Common Terminology Criteria for Adverse Events) version 4.0.
- The methylation status of *BRCA* 1 and 2 promoters will be measured in germline DNA from blood cells at the beginning of the study and after PD, or at the end of study treatment by other reason, and in paired primary and metastatic lesions. It will be analysed: 1) changes of germline methylation pre- and post-treatment; 2) correlation between germline methylation status and efficacy outcome data; 3) correlation between germline and somatic methylation status and 4) correlation between primary and metastatic lesions.

## 6.2 Exploratory End-points

The following exploratory end-points could be studied:

- Biomarker values from the primary or metastatic tumour tissue could be used for assessment of biomarkers related to breast tumour sensitivity and/or resistance to olaparib (e.g. may include but not limited to somatic *BRCA1/2* mutational status or other genes related to cancer susceptibility or thought to be related to the drug mechanism of action). These samples will be instrumental to explore biomarkers of response or resistance to olaparib.
- DNA and RNA obtained from the blood samples collected during the study may be used for potential pharmacogenomics analyses related to drug response or adverse drug reactions (including but not limited to comparison of germline DNA or RNA patterns of patients who respond well and those who respond poorly to treatment). For example, genes coding drug metabolizing enzymes, drug transport proteins or genes involved in DNA repair pathways, cancer susceptibility or thought to be related to the drug mechanisms of action may be analysed.
- Specific mutations or epigenetic biomarkers identified in pre-therapy tumour specimens as potentially linked to treatment response could be tested in plasma DNA. A targeted NGS panel may be designed to study all the candidate mutations. Plasma DNA has also the potential to be a surrogate of tumour load and may also be instrumental to monitor disease.

## 7. DATA SCREENING AND ACCEPTANCE.

## 7.1 Missing data

The frequency of missing data will be examined and reported for each variable in the analysis. We will not perform data imputation for missing data.

### 7.1.1 Missing date

If the day of the month is missing for any date used in a calculation, the 15th of the month will be used to replace the missing date unless the calculation results in a negative time duration (e.g., date of onset cannot be prior to day one date). In this case, the date resulting in 1 day duration will be used. If the day of the month and the month are missing for any date used in a calculation, the date will be considered missing.

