#### **9.2.1.2 Analysis of Secondary Endpoints**

The secondary efficacy endpoints are:

**Clinical Benefit Rate (CBR):** A patient will be considered to have CB if the patient has a sustained complete response (CR) or partial response (PR), or stable disease (SD)  $\geq 24$  weeks according to RECIST version 1.1 definitions. Otherwise, the patient will be considered as not achieving CB in the CBR analysis.

CBR will be estimated by dividing the number of patients with CR, PR, or SD  $\geq 24$  weeks by the efficacy population.

$$\text{Clinical Benefit Rate} = \frac{\text{Number of CRs + PRs + SD} \geq 24 \text{ weeks}}{\text{Efficacy Population}}$$

The CBR will be reported, including a 95% confidence interval.

For the CBR analysis in the ITT population, patients with inadequate data for tumour assessment (e.g., no baseline assessment or no follow-up assessments) will be considered as not achieving CB in the CBR analysis.

**Duration of Response (DoR):** DoR is defined as the time from the first documentation of objective tumour response (CR or PR) to the first documented PD using RECIST version 1.1, or to death due to any cause, whichever occurs first. DoR data will be censored on the date of the last tumour assessment on study for patients who do not have objective PD and who have not died due to any cause while on study. Additionally, patients who start a new anti-cancer therapy prior to documented PD will be censored at the date of the last tumour assessment prior to the start of the new therapy.

RD will only be calculated for the subgroup of patients with an objective response.

**Progression-Free survival (PFS):** PFS is defined as the time from study enrolment to the first documented PD, using RECIST version 1.1, or death from any cause, whichever occurs first. PFS data will be censored on the date of the last tumour assessment on study for patients who do not have objective PD and who have not died due to any cause while on study. Additionally, patients who start a new anti-cancer therapy prior to documented PD will be censored at the date of the last tumour assessment prior to the start of the new therapy.

The analyses of PFS will be performed in the ITT and Efficacy populations. PFS time will be summarized for the ITT population using the Life tables and displayed graphically where appropriate. Confidence intervals (CIs) for the 25th, 50th and 75th percentiles of the event free time will be reported.

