**Overall Survival (OS):** OS is defined as the time from the date of study enrolment to the date of death from any cause. OS data will be censored on the last date the patient is known to be alive.

OS will be analysed in the ITT and Efficacy population. The median event times and 95% CIs will be estimated.

All of the above secondary analyses will be conducted at a two-sided 0.05 level of significance.

The secondary time-to-event endpoints (RD, PFS, OS) will be summarised using a Kaplan-Meier analysis and associated curves.

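### The partial-date rule in SAP 7.1.1 is not bounded by a patient's other known dates, so a partial date can reorder or drop events in PFS, DoR, OS and the post-treatment AE tables (minor)

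*SAP*

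**What the plan says.** SAP 7.1.1 has one rule for all variables. Its scope is stated as "If the day of the month is missing for any date used in a calculation". The 15th "of the month will be used to replace the missing date unless the calculation results in a negative time duration", and for that exception: "In this case, the date resulting in 1 day duration will be used". Its example of the exception is an onset date before day one. If more is missing: "If the day of the month and the month are missing for any date used in a calculation, the date will be considered missing". SAP 7.1 adds: "We will not perform data imputation for missing data".

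Three analysis rules use these dates.

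- **PFS and DoR (SAP 9.2.1.2).** The order of new therapy and progression decides the outcome: "patients who start a new anti-cancer therapy prior to documented PD will be censored at the date of the last tumour assessment" before that therapy. The basic censoring rule for patients without progression covers only those "who have not died due to any cause while on study".
- **OS (SAP 9.2.1.2).** "OS data will be censored on the last date the patient is known to be alive".
- **AEs (SAP 9.2.2).** Events count if they start on treatment or within 30 days of the last dose.

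Neither document requires an imputed death to fall on or after last contact, or an imputed therapy start to be checked against a documented progression.

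**The concern.** The guard looks only at whether a duration turns negative. PFS, DoR and OS run from enrolment or first response, usually months earlier, so an imputation can be wrong by up to 16 days and contradict another recorded date while every duration stays positive. Four failures can follow when a date is partial:

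1. New therapy is dated before a progression scan done after the 15th of the same month. The progression becomes a censoring one scan interval (8 weeks) earlier.
2. A death is dated before the patient was last seen alive.
3. A death with unknown month has no event time for OS. If there was no earlier progression it has none for PFS either, and the basic PFS censoring rule does not cover it because the patient has died.
4. An AE that began within 30 days of last dose is moved past day 30 and leaves the safety tables.

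PFS, DoR and OS are named secondary endpoints in about 34 patients. If the plan is silent, such conflicts are settled during programming, with single-arm outcome data in view.

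**Working it through.** **Reproducing the plan's own figure.** SAP 7.1.1 gives no number. The stated figure that depends on dated deaths is in Protocol 3.2: more than 50% of deaths by 30 months after first enrolment. Inputs from that section: median OS 12 months, accrual 24 months. Assume exponential survival and uniform accrual, so follow-up runs from 6 to 30 months:

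P(dead) = 1 - [12 / (24 ln 2)] x (2^-0.5 - 2^-2.5) = 1 - 0.7213 x (0.7071 - 0.1768) = 0.617

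That is 0.617 x 34 = 21.0 deaths, in agreement with the protocol.

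**Failures 1 and 2: wrong order when the day is missing.** Let the reference date be the progression scan or last contact, and let the true date follow g days later. The order is reversed only if the reference date is after the 15th and the true date is in the same month. A month of L days has L - 15 - g such reference dates (none if negative). With calendar dates uniform over a 365-day year (assumption):

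P(g) = sum over months of max(0, L - 15 - g) / 365

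- g = 1: (365 - 12 x 16)/365 = 173/365 = 47%
- g = 7: (365 - 12 x 22)/365 = 101/365 = 28%
- g = 14: (7 x 2 + 4 x 1)/365 = 18/365 = 5%
- g of 16 or more: 0%

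The numerators for g = 1 to 15 add to 1,338, and for g = 7 to 15 to 480. Averaged over a uniform gap:

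- 1-30 days: 1,338/365/30 = 12%
- 7-42 days: 480/365/36 = 3.7%
- 23-37 days: 0%

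The same figures come from applying the rule to every calendar day of four years. For deaths with a contact-to-death gap of 1-30 days, the reversed cases are dated on average 5.5 days, and at most 15 days, before last contact.

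**Illustrations (invented dates).**

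- Enrolled 10 January 2019, scan 25 March, progression 20 May, new therapy 28 May but recorded only as May. The rule gives 15 May, before progression. The patient is censored at day 74 instead of having an event at day 130. Enrolment to 15 May is 125 days, so the guard does not act.
- Same enrolment, last contact 27 August (day 229), death 29 August (day 231) but recorded only as August. The rule gives 15 August, day 217, which is 12 days before last contact.

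**Failure 1 at trial level.** Assume median PFS 3.7 months (close to the 3.68 months in Protocol Table 4 for the breast cohort of study D0810C00042), 8-weekly scans and a gap of 1-30 days. If 5% / 10% / 20% of therapy starts lack the day (assumed), simulation gives 0.2 / 0.4 / 0.8 of 34 progressions turned into censorings, and median PFS rises by about 1 / 2 / 4 days. With a 7-42 day gap, the expected number at 5% to 20% is 34 x 0.05 x 0.037 = 0.06 to 34 x 0.20 x 0.037 = 0.25.

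**Failure 3.** If 5% / 10% / 20% of deaths lack the month (assumed), about 19.9 / 18.9 / 16.8 of the 21.0 deaths keep an event date. The simulated median OS of about 12.3 months becomes 13.0 / 13.7 / 15.1 if those patients are censored at last contact (taken as up to 2 months before death), or 12.7 / 13.1 / 13.9 if they are excluded. The SAP does not say which applies.

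**Failure 4.** For onset uniform over the 30 days after last dose and a missing day, the 15th of the onset month falls after day 30 in about 11% of cases.

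**The case against.** The strongest reply is about timing. Protocol 3.2 and Attachment 1 put the post-treatment visit 30 (+/-7) days after last dose and require it before any new anticancer therapy. If the last dose is close to the progression scan, the planned gap is about 23-37 days, and at that gap the order cannot be reversed. This stands, and it makes failure 1 uncommon. It does not remove it, because the visit may be brought forward when therapy cannot wait, with no minimum interval.

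Data quality is the second reply. Sites take end-of-treatment samples before the next regimen (Protocol Table 13), the death date is an eCRF item, queries are raised, and SAP 7.1 requires missingness to be reported for each variable. Partial dates may be few. That also stands. That therapy and death dates are the ones most often partial is plausible, since they are collected after scheduled visits end, but the documents do not show it.

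A reader might infer more than the documents support:

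- *PFS and OS are systematically overstated.* Failures 1 and 3 push upward, but failure 2 keeps the event and shortens OS.
- *A quarter of progressions would be lost.* The rate is 26% only for gaps of 1-14 days, and only among therapy starts with a missing day.
- *Deaths disappear from the report.* A year-only death lacks an event date for OS or PFS, but OS can be censored at last known alive, and the death can still be counted in the all-cause mortality table (SAP section 10, table 3.2.1).
- *Adverse events in general are dropped.* Only those starting in the 30 days after last dose are exposed.

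**Conclusion.** The point holds in conditional form: when a date is partial, SAP 7.1.1 can produce a sequence that contradicts the patient's own record, and nothing else in the two documents prevents it. That conclusion rests on the text and does not depend on the simulations.

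The size is small or unknown. Failure 1 amounts to less than one patient of 34 under every assumed share up to 20% of therapy starts. Failure 2 is an error of at most 15 days per affected death. Failure 3 can move median OS most, but only if deaths with unknown month are common. Failure 4 touches about 11% of post-treatment AEs with a missing day. Gaps, calendar uniformity and shares of partial dates are all assumptions.

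The effect is confined to PFS, DoR, OS and the post-treatment AE tables. The primary decision, at least 14 responders, is a count and uses none of these durations. Severity: minor.

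**What to change.** Replace the single rule in SAP 7.1.1 with imputations bounded by known dates:

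- **Death, day missing.** Use the later of the 15th and the day after last known alive, within the recorded month. In the illustration this gives 28 August, day 230, against a true 231.
- **Death, only the year known.** Count it as an event in OS, and in PFS or DoR where no progression came first. Date it within the recorded year and after last known alive, for example at the midpoint of the feasible interval, with a sensitivity analysis at both ends. The day after last known alive is not a safe default: last contact in November 2018 with death recorded as 2019 would then be dated in the wrong year.
- **New anti-cancer therapy, day missing.** Never before last dose. If the month is that of a documented progression and nothing in the record shows that therapy came first, use the day after that progression, with a sensitivity analysis using the 15th. The condition keeps the new-therapy censoring rule working where therapy really did come first.
- **AE onset.** Treat as inside the 30-day window whenever the known month and year allow it.

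The cost is one SAP paragraph and minor programming. It should be settled before the database lock, so that the choices do not depend on the data.

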## 7.2 Statistical software

The statistical analysis will be developed in SAS Enterprise Guide v7.1.

## 7.3 Database lock

The first database lock will be carried out when enough data have been obtained to perform the step 1 analysis of the optimal two stage Simon model.

The database lock for efficacy analysis will be carried out when there will be sufficient data to achieve the primary and secondary objectives or at the date of last patient's death or withdraw of the informed consent, whichever comes first. As the study design is two Stage Simon design, if in step 1 we do not obtain the enough responses the data base will be closed and perform the primary analysis.

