3.2. Duration of the Study

It is estimated that the patient recruitment will be completed approximately in 24 months.

All patients included will receive study therapy until radiographic or symptomatic progression, unacceptable toxicity or withdraw of the informed consent, whatever occurs first, this is the active treatment phase. Patients discontinuing the study treatment will enter the follow-up phase.

For safety reasons all patients will have a visit 30 (+/-7) days after finishing treatment with the study drugs/medications. This post-treatment visit must be performed before starting with any new anticancer therapy; however, in case the beginning of this new therapy cannot be delayed as per the investigator's judgment, the safety visit may be performed in advance, but always before starting with the new anticancer therapy.

All patients will be followed till death or data cut-off date to evaluate the OS objective.

The start date of study is the date of the first site initiation visit. The data cut-off date will be the date of last patient's death or withdraw of the informed consent or the date when there is sufficient data to achieve the primary and secondary objectives, whichever comes first. It is estimated that the final analysis could be performed approximately 30 months after the enrolment of the first patient because, considering a median OS of 12 months, it is estimated that more than 50% of death events will have occurred at that time and overall survival analysis could be performed.

The study will be considered complete following the data cut-off date and data-lock for the final analysis. Performing exploratory objectives will be independent of the date of the end of the study.

4. Study Population

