6.1.1. Primary Efficacy Assessments

The primary efficacy variable is Objective Response Rate (ORR).

Tumour response will be assessed using RECIST v.1.1. Tumour assessment will be performed at baseline; the same method of measurement used at baseline will be used for further assessments, which will be conducted every 8 weeks (+/- 1 week). Responses should be confirmed according to RECIST v.1.1 after at least 28 days.

The best response across treatment will be recorded. ORR is defined as the percentage of patients with a complete or partial response out of the total of patients in the considered study population (refer to section 8.2.1. Patient Populations).

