8.1. Determination of Sample Size

8.1.1. Sample Size Determination

We have set the null hypothesis (H0) that ORR will be 30% (ORR achieved by TN patients treated with gemcitabine plus carboplatin¹) versus the alternative hypothesis (H1) that ORR will be 54% (ORR showed by TN *BRCA* mutated patients treated with olaparib²). Using an optimal two-stage Simon model and considering an alpha error of 0.05 and a statistical power of 80%, it will be required to include 31 evaluable patients. Twelve evaluable patients will be enrolled in the first stage, and if at least 4 patients of them have response, additional patients will be recruited to get a total of 31 evaluable patients. Assuming a 10% dropout rate, the total number of patients to be enrolled is 34. Considering, these data the number of responders needed at the end of stage 2 to reject the null hypothesis is at least 14 responders.

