Exploratory subgroup analysis may be performed if deemed appropriate.

8.2.10. *Interim Analysis*

There is no planned any interim analysis.

The optimal two stage Simon Model is carried out in two steps. The purposes of the step 1 analysis is to allow early stopping of the study for futility.

Following the two-stage Simon design, it will be reviewed whether 4 of the first 12 evaluable patients show tumour response according to RECIST v.1.1, and if this occurs, additional patients will be included to get a total of 34 patients.. If 3 or less than 3 patients of the first 12 evaluable patients show an OR, recruitment will be stopped.

8.2.11. *Criteria for End of Study*

This study will be considered complete following the data cut-off date and datalock for the final analysis. The data cut-off date for the final analysis will occur after all enrolled patients have died or withdraw of the informed consent or there is sufficient data to achieve the primary and secondary objectives, whatever occurs first. It is estimated that the final analysis could be performed approximately 30 months after the enrolment of the first patient because, considering a median OS of 12 months, it is estimated that more than 50% of death events will have occurred at that time and overall survival analysis could be performed. If further data are collected that are not included as part of the final locked

database, the post-lock data will eventually be combined with the locked database and stored in a data library separate from the locked database.

Performing exploratory objectives will be independent of the date of the end of the study.

9. Informed Consent, Confidentiality, Responsibility Insurance and Regulatory Considerations

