### 3.1 Sample Size

We have set the null hypothesis (H0) that ORR will be 30% (ORR achieved by TN patients treated with gemcitabine plus carboplatini) versus the alternative hypothesis (H1) that ORR will be 54% (ORR showed by TN *BRCA* mutated patients treated with olaparibii). Using an optimal two-stage Simon model and considering an alpha error of 0.05 and a statistical power of 80%, it will be required to include 31 evaluable patients. Twelve evaluable patients will be enrolled in the first

stage, and if at least 4 patients of them have response, additional patients will be recruited to get a total of 31 evaluable patients. Assuming a 10% dropout rate, the total number of patients to be enrolled is 34. Considering, these data the number of responders needed at the end of stage 2 to reject the null hypothesis is at least 14 responders.

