### 9.2.1.1 Analyses of Primary Endpoint

The primary endpoint is ORR.

**Objective Response Rate (ORR):** A patient will be considered to have achieved an objective response (OR) if the patient has a complete response (CR) or partial response (PR) according to RECIST version 1.1 (4) definitions. Otherwise, the patient will be considered as non-responder in the ORR analysis. ORR will be estimated by dividing the number of patients with objective response (CR or PR) by the **Efficacy** population ("response rate").

$$\text{Objective Response Rate} = \frac{\text{Number of CRs + PRs}}{\text{Efficacy Population}}$$

The ORR will be reported, including a 95% confidence interval using the Clopper-Pearson method (5).

These analyses will be conducted at a two-sided 0.05 level of significance.

The number of responders needed at the end of stage 2 to reject the null hypothesis is at least 14 responders.

Additional sensitivity analyses will be done with the ITT population. For the analysis in the ITT population, patients with inadequate data for tumour assessment (e.g., no baseline assessment or no follow up assessments) will be considered as non-responders in the ORR analysis.

In addition, the best objective response (BOR) for each patient will be summarized.

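### SAP 7.3 closes the database after a failed stage 1 without a cut-off or minimum follow-up, and this is not reconciled with the protocol, which stops recruitment only and follows patients for survival

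*SAP*

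**What the plan says.** SAP 7.3 describes two locks: a first one when there is enough data for the step 1 analysis, and an efficacy lock when data suffice for the primary and secondary objectives or at the last death or consent withdrawal. It then adds that "if in step 1 we do not obtain the enough responses the data base will be closed and perform the primary analysis". It does not say when this closure happens, or what follow-up the treated patients have by then.

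The other sections describe the same branch differently:

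- Protocol 8.2.10, Interim Analysis: "If 3 or less than 3 patients of the first 12 evaluable patients show an OR, recruitment will be stopped". SAP 8 has the same rule and the same consequence. It adds that, after a stop, the feasibility and interest of some secondary and exploratory analyses will be reviewed in light of the patients and samples available.
- Protocol 3.2: "All patients will be followed till death or data cut-off date to evaluate the OS objective". The cut-off is the last death or consent withdrawal, or the point at which data suffice for the primary and secondary objectives, whichever is first. No exception is made for a futility stop.
- Protocol 6.1.1, on the primary endpoint: "The best response across treatment will be recorded". Scans are every 8 weeks, and responses are to be confirmed after at least 28 days.

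**The concern.** If closure simply waited for the ordinary efficacy lock, the last sentence of SAP 7.3 would add nothing. Its natural reading is therefore a lock tied to step 1, and nothing in the SAP prevents that lock from falling soon after the twelfth evaluable patient. The consequences would be:

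- **OS** would be immature, although it is a stated secondary endpoint and the reason Protocol 3.2 gives for continued follow-up.
- **ORR** would be frozen while some patients are still on treatment. A stable patient who responds later would be counted as a non-responder. No accrual pause is stated, so a recently enrolled patient with no scan yet could fall outside the Efficacy population (SAP 4.2) and count as a non-responder in the ITT analysis (SAP 9.2.1.1).
- **Safety** summaries run to 30 days after the last dose (SAP 9.2.2). For patients still on drug at the lock, later events would miss that analysis.

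After a futility stop, these patients are the main evidence the trial leaves about olaparib in this population, so the branch needs a defined end.

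**Working it through.** **Inputs from the documents.** Response rates of 30% (H0) and 54% (H1), alpha 0.05, power 80%, 31 evaluable and 34 enrolled patients (Protocol 8.1.1, SAP 3.1). Stop at 3 or fewer responders in 12 (Protocol 8.2.10, SAP 8). Accrual over about 24 months, median OS 12 months, final analysis at about 30 months (Protocol 3.2). Olaparib PFS medians in breast cancer of 54 days (1.77 months) and 3.68 months (Protocol Table 4) and 7.0 months (OlympiAD, Protocol 1.4.5.1).

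**Assumptions not in the documents.** Uniform accrual, exponential event times, the first 12 enrolled all evaluable, and a lock 2 to 6 months after the twelfth entry. One 8-week scan plus a 4-week confirmation takes 12 weeks, which lies inside that range.

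**Plan's own figures.** An exact search for the optimal Simon design with these inputs gives 12 patients in stage 1, 31 in total and rejection at 14 or more, as printed. It stops at 4 or fewer in stage 1, whereas the documents stop at 3 or fewer. That is a separate matter, and I use the printed rule below.

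For event maturity, let λ = ln 2 / median, A = accrual time and a = time from last entry to lock. The expected proportion with an event is

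1 − [exp(−λa) − exp(−λ(a + A))] / (λA).

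For the full trial, λ = ln 2 / 12 = 0.0578, A = 24 and a = 6. This gives 1 − (0.7071 − 0.1768)/1.3863 = 61.7%, about 21 of 34 deaths. It agrees with the plan's estimate of more than 50% at 30 months.

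**Probability of the branch.** P(X ≤ 3 | n = 12, p = 0.30) = 0.0138 + 0.0712 + 0.1678 + 0.2397 = 0.4925. At p = 0.54 it is 0.0415.

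**Maturity at the lock.** Twelve patients enter in A = 24 × 12/34 = 8.47 months, so λA = 0.489 for OS. With a = 2: 1 − (0.8909 − 0.5462)/0.489 = 29.5%. With a = 6: 1 − (0.7071 − 0.4335)/0.489 = 44.1%. Month 30 means a = 30 − 8.47 = 21.5, which gives 77.2%.

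| Lock after twelfth entry | Deaths (of 12) | PFS events, median 1.77 mo | 3.68 mo | 7.0 mo |
|---|---|---|---|---|
| 2 months | 29.5% (3.5) | 86.7% | 65.7% | 44.5% |
| 3 months | 33.5% (4.0) | 91.0% | 71.6% | 49.7% |
| 4 months | 37.2% (4.5) | 93.9% | 76.5% | 54.4% |
| 6 months | 44.1% (5.3) | 97.2% | 83.9% | 62.6% |
| 21.5 months (month 30) | 77.2% (9.3) | – | – | – |

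The longest possible follow-up at such a lock is 8.5 + 2 = 10.5 to 8.5 + 6 = 14.5 months, against an assumed median OS of 12 months. The median would either not be reached or be read from the thin end of the curve.

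**The case against.** The strongest reply is that this is a gap, not a breach. SAP 7.3 gives no timing, and its preceding sentence ties the efficacy lock to sufficient data for both sets of objectives. Protocol 8.2.10 and SAP 8 describe step 1 as allowing the study to be stopped early for futility. Protocol 4.4.3 lets the sponsor discontinue on new effectiveness information. Protocol 3.2 follows patients to death or cut-off, and sufficient data is left undefined. Both documents allow the SAP to modify protocol plans. SAP 8 provides a review of secondary analyses after a stop, which is not unreasonable with about 12 patients.

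Most of this stands, and it limits the point. A reader might infer the following, none of which the documents support:

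- *The SAP orders an immediate lock.* It does not say so. It only fails to exclude one.
- *OS, PFS and response duration would all be unanswerable.* PFS would have about 45% to 97% events. Response duration rests on at most 3 responders among the 12 whenever the lock falls.
- *The plan requires more than 50% deaths.* Protocol 3.2 offers that as an estimate explaining the 30-month timing, not as a threshold.
- *Data arriving after the lock are discarded.* Protocol 8.2.11 says they will eventually be combined with the locked data and stored separately, although it commits to no analysis of them.
- *Safety surveillance ends.* Related serious events are collected even after study closure, and MDS/AML and new malignancies are reportable in long-term follow-up (Protocol Attachment 4). What could be lost is their inclusion in the planned analysis.

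The reply does not supply a cut-off. The SAP 8 review turns on numbers of patients and samples, not on length of follow-up, and SAP 7.3 does not say that it is modifying Protocol 3.2.

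**Conclusion.** The point holds as an unreconciled gap with a material consequence. One SAP sentence closes the database on a failed step 1. The other sections stop recruitment only and keep survival follow-up open, and none defines when follow-up ends in this branch. The branch is about as likely as not under H0 (0.49) and unlikely under H1 (0.04).

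If the lock follows soon after stage 1, OS would have roughly 3.5 to 5.3 deaths among 12 patients, instead of about 9.3 at month 30, and the reported ORR would rest on best responses that are not final. The direction holds across the whole range of lags examined, but the percentages depend on the assumed lag, uniform accrual and exponential survival. Even the mature OS estimate would be imprecise with 12 patients. The go/no-go decision itself is not affected.

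**What to change.** Reword SAP 7.3 so that:

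1. The existing first lock serves as the data cut for the go/no-go decision. If step 1 fails, recruitment stops, and the decision stands whatever responses are seen later.
2. Patients already treated remain under the existing protocol assessments and survival follow-up until the Protocol 3.2 cut-off.
3. There is one final lock, at which ORR on final best response, PFS, OS and safety are analysed, with response duration described only.

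Align SAP 8 by naming the secondary endpoints that will be reported after a stop. Feasibility review can stay for the biomarker and exploratory analyses.

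The cost is SAP wording, a later final report, and longer survival follow-up of the few patients already treated. If the cut-off fell at month 30, the lock would come about 15.5 to 19.5 months later than one taken 6 or 2 months after the twelfth entry (21.5 − 6 and 21.5 − 2). It would come sooner if the Protocol 3.2 conditions were met earlier.
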